### **Environment and Preliminary Studies of Direct Relevance to the Proposed Work:**

Our interdisciplinary team represents experts in nursing, respiratory physiology, pulmonology, symptom management, biostatistics, and information technology. Since coming to MUSC in 8/2016, [name] has established collaborative relationships with researchers and clinicians while working with TACHL.

**Experience in mHealth Development:** [name] has significant experience in smart phone app development, software, server and peripheral hardware interface development. [name] has significant experience in measurement of objective and subjective breathing responses.

**Experience in clinical COPD research:** [name] has conducted numerous clinical COPD studies. [name] has conducted studies analyzing biomarkers in COPD. [name] has conducted several laboratory studies in pediatric and adult populations, including adults with COPD and anxiety.

## **4.0 Study Endpoints**

Study end points include: Successful study completion, participant consent withdrawal, and PI termination due to failure to adhere to the protocol, loss of contact with the patient, and/or unexpected adverse events.

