### **Exclusion Criteria**

- Pregnant female or less than 1 year post-partum; or
- Diagnosed cognitive deficit or observed lack of understanding during the informed consent process; or
- Mobility impairment; or
- Lack of 3g WiFi access in place of residence; or
- Unwillingness to wear physical activity tracker daily, follow protocol, and/ or attend study visits.

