## 12.0 Data Management

**Statistical Analysis:** Primary analyses for this pilot feasibility study center on patient satisfaction, treatment fidelity and adherence, with a secondary focus on changes observed on fatigue and dyspnea scales (obtained from the SGRQ), PImax and PEmax change, physical activity (steps per day and active hours per day), physical activity engagement (PROMIS activity engagement scale), and sex based differences. Treatment satisfaction will be measured qualitatively through analysis of recorded post-intervention interviews. Training frequency will be automatically assessed by the Bluetooth enabled tracker, which will also be developed to measure pressure changes to evaluate treatment gains for PImax and PEmax. Pre- and post-intervention data will be analyzed for correlation between symptom severity and respiratory muscle strength (PImax and PEmax) along with mean steps per day. Post-Intervention data collection will include PEmax, PImax, PROMIS and SGRQ scales (see above) to compare to baseline measures. The sample will be characterized using descriptive statistics for all variables, as appropriate. T-tests or non-parametric Wilcoxon rank sum tests will be used to compare continuous demographic and baseline clinical variables and chi-square or Fisher's Exact Test will be used for categorical (e.g., survey responses). An overall indicator of acceptability/usability will also be a) adherence via a % of total EMA assessments completed. Comparisons between device use and reported affective states, stress levels, COPD symptoms over previous 1-2 days will also be examined. We will also gather information from the post-trial interviews via qualitative analyses on aspects of the SAM program that would benefit from refinement. Qualitative data will be presented as themes of domains relevant for refinement of SAM. Exploratory Quantitative Analyses: Nonparametric analyses will compare emergency department visits and hospitalizations with SAMS EMA question responses. Comparisons will be run on EMA ratings and training use.

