#### **14.0 Withdrawal of Subjects**

Participants may voluntarily elect to withdraw their consent at any time for any or no given reason while enrolled in the study. The PI may withdraw participants from the study at any time if they decide it is in the participant's best interest, if they do not follow the investigator's instructions, and/or if they fail to maintain contact with the researchers or attend study visits. Withdrawals of participants may also occur if there is a protocol violation or early study closure. All data gathered from withdrawn participants will be used in the analysis plan under an Intention-to-Treat (ITT) model.

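### The investigator may end participation for non-adherence, itself a primary outcome; this cuts short the observation of poor adherers and leaves the adherence denominator undefined.

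*Combined protocol and SAP*

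**What the plan says.** Section 4.0 (Study Endpoints) lists "PI termination due to failure to adhere to the protocol" as one way a participant's study can end. Section 14.0 (Withdrawal of Subjects) gives the investigator discretion to withdraw participants for several reasons, among them "if they do not follow the investigator's instructions, and/or if they fail to maintain contact with the researchers or attend study visits". Neither section says how much non-adherence is enough.

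Section 12.0 (Statistical Analysis) states: "Primary analyses for this pilot feasibility study center on patient satisfaction, treatment fidelity and adherence". It names one adherence indicator, "adherence via a % of total EMA assessments completed", and takes training frequency from the Bluetooth tracker. On satisfaction it says: "Treatment satisfaction will be measured qualitatively through analysis of recorded post-intervention interviews".

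For people who leave early, Section 14.0 says: "All data gathered from withdrawn participants will be used in the analysis plan under an Intention-to-Treat (ITT) model". The safety plan under Section 13.0 adds accrual and attrition reports (Section B.3) and a review of adherence and barriers to retention (Section F).

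**The concern.** The trigger for ending participation is a low value of something the trial exists to measure. Once participation ends, no further training sets, EMA entries or visits are provided for. The intention-to-treat sentence covers data that exist; it cannot supply data that the termination prevented.

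This matters because Section 12.0 (Sample Size) gives demonstrating feasibility as the purpose, and Section 1.0 says the results will shape the app and procedures for a large efficacy trial. How many people fail to adhere, by how much and why is the main information sought. The people who could best supply it are those whose observation may be cut short. If adherence is then computed over time enrolled, the reported figure can look better than one set against the planned six weeks.

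**Working it through.** **1. What an early termination stops, outcome by outcome**

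- Training adherence and fidelity: tracker and diary records end at exit. The documents do not say whether the remaining planned sets count as missed or leave the denominator.
- EMA adherence: the percentage is of a total that is not defined. It could be all EMAs scheduled over six weeks or only those sent while enrolled.
- Satisfaction: it rests on interviews after the intervention. None is specified for someone terminated early.
- Symptom and strength change: Section 12.0 promises intention-to-treat estimates of change from before to after treatment. A participant ended before week 6 has no later value, and no method for missing data is given.

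**2. The plan's own precision figure**

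Inputs from Section 12.0 (Sample Size): SD of change 0.5 to 2.0, about 25 completers of 30 recruited. Half-width of a 95% interval = 1.96 × SD / √n.

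- n = 25: 1.96 × 0.5 / 5 = 0.196 and 1.96 × 2.0 / 5 = 0.784. These match the stated 0.20 and 0.78.
- n = 30: 0.179 and 0.716, which do not match.

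So the stated precision fits the expected completers, with attrition of 5/30 = 16.7%. Non-completers contribute no change score to that calculation. The point about termination does not depend on this figure.

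**3. The full denominators**

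Section 10.0 plans 5 sets a day, 5 days a week, for 6 weeks: 5 × 5 × 6 = 150 sets per trained participant. If one EMA a day is meant, 7 × 6 = 42 EMAs are scheduled per participant assigned EMA.

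**4. Illustration**

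Only the arm size of 15 comes from the documents. Assumed: k participants adhere at 20% and are terminated after week 2 of 6; the other 15 − k adhere at 80%.

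- Full schedule, sets after exit counted as not done: [(15 − k) × 0.80 + k × 0.20 × 2/6] / 15
- Mean of per-person rates while enrolled: [(15 − k) × 0.80 + k × 0.20] / 15
- Sessions pooled while enrolled: [(15 − k) × 0.80 × 6 + k × 0.20 × 2] / [(15 − k) × 6 + k × 2]

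For k = 3:

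- Full schedule: (9.6 + 0.2) / 15 = 65.3%
- Per-person mean: (9.6 + 0.6) / 15 = 68.0%
- Pooled: (57.6 + 1.2) / 78 = 75.4%

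| Terminated (k) | Full schedule | Per-person mean | Pooled sessions |
|---|---|---|---|
| 1 | 75.1% | 76.0% | 78.6% |
| 3 | 65.3% | 68.0% | 75.4% |
| 5 | 55.6% | 60.0% | 71.4% |

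With 3 terminated, the excess over the full-schedule figure is 2.7 points (per-person) or 10.1 points (pooled). Varying the assumptions (1 to 5 terminated, exit after week 1, 2 or 3, adherence of 70% to 90% in the others, 20% held for those terminated) gives 0.7 to 5.6 points per-person and 2.3 to 23.5 points pooled.

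The per-person gap needs a caution. The 68.0% is also what would be seen over six weeks if the three had stayed and continued at 20%. That gap therefore comes from counting the weeks after exit as zero. The pooled figure is different: it gives poor adherers less weight because they were ended early.

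**The case against.** The strongest reply is that the plan already protects the analysis. Section 14.0 retains withdrawn participants' data, attrition is reported, and adherence and retention are reviewed. The power is discretionary, and its frequency is unknown. It may be rare, because entry already excludes people for "Unwillingness to wear physical activity tracker daily, follow protocol, and/ or attend study visits". The instruction-following clause is not limited to missed sessions; it could cover safety instructions. And this is a pilot that disclaims any test of effectiveness.

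Most of that stands, and it rules out three stronger readings:

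- A reader might infer that the trial removes its own failures from the analysis. The documents say the opposite: gathered data are kept. A completers-only adherence figure (80% in the illustration, 14.7 points above 65.3%) is an analysis that nobody has planned.
- A reader might infer that retention is inflated. A terminated participant is a non-completer, so termination lowers the completion rate.
- A reader might infer that the worst adherers will be ended systematically. No threshold or automatic removal is stated, so this cannot be shown.

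What the reply does not meet is narrower. Retained data stop at the exit, attrition counts do not supply adherence, satisfaction or week-6 values, and the denominator remains open.

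**Conclusion.** The point holds in a limited form, with moderate severity. Sections 4.0 and 14.0 allow a primary outcome to trigger the end of its own measurement, with no threshold. Observation of poor adherers can be cut short, although what was recorded before exit is used.

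Adherence can be overstated if it is computed over time enrolled. The excess is small with per-person means and larger with pooled sessions; Section 12.0 specifies neither. All rates in the illustration are assumed, so the ranges show how far the choice of denominator matters and do not predict the bias. The lost interviews and the lost week-6 and week-14 outcomes follow directly from an early termination, but how many would be lost cannot be derived from the documents.

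**What to change.** 1. In Sections 4.0 and 14.0, state that non-adherence to training, EMA or the activity tracker is not by itself a reason to end study follow-up. Leave consent withdrawal, best-interest withdrawal and adverse-event termination unchanged. This concerns follow-up and counting only, not who should continue training.
2. Continue to invite non-adherent participants to the week-6 and week-14 assessments and to the interview, unless they withdraw consent.
3. In Section 12.0, define training adherence over all participants randomised to training, against the full 150 planned sets. Define EMA adherence over all participants assigned EMA, against all EMAs scheduled over six weeks. Count anything after an exit as not done in both.
4. Report any investigator terminations by arm and reason.

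The cost is wording changes in three sections, a few extra follow-up contacts and an adherence figure that may be less favourable. The visits are already scheduled, and Section 10.0 states a $50 participant payment for each of the week-6 and two-month visits; the documents give no staffing cost.

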## **5.0 Inclusion and Exclusion Criteria/ Study Population**

Potentially eligible participants will be identified through a combination of a medical chart review, use of breathing symptom survey, and a Pulmonary Functioning Test (PFT) - if there is not one on record within the past 6 months.

### **Inclusion Criteria**

- 40 years of age or older; and
- Able to read and write English; and
- Diagnosed with COPD (PFT values: FEV1/FVC <0.7 and FEV1% predicted < 80% - within the past 6 months); or Dyspnea score of greater than "2" on the Modified Medical Research Council (MMRC) questionnaire.

### **Exclusion Criteria**

- Pregnant female or less than 1 year post-partum; or
- Diagnosed cognitive deficit or observed lack of understanding during the informed consent process; or
- Mobility impairment; or
- Lack of 3g WiFi access in place of residence; or
- Unwillingness to wear physical activity tracker daily, follow protocol, and/ or attend study visits.

### *Inclusion of a diverse population*

COPD is not a population specific disease. Participants from all racial and ethnic backgrounds will be encourage to volunteer as participants. However, pregnant females and females less than 1 year post-partum (via self-report) will be excluded, as pregnancy affects fatigue and the perception of dyspnea due to increased abdominal pressure on the diaphragm and potential displacement of abdominal organs.

### *Exclusion of children*

COPD is a disease primarily exclusive to late adulthood. Children are therefore excluded from this study.

## 6.0 Number of Subjects

N= 30 adult participants.

## 7.0 Setting

This is not a multi-site trial. All aspects of this study will take place on-campus at MUSC or at the participant's place of residence. Informed consent will be conducted in the privacy of a patient room. The initial baseline and final study visits will occur at SCTR Nexus Research Center. All other study visits will be conducted either electronically over the tablet or by phone with the participant at their place of residence.

## 8.0 Recruitment Methods

Study recruitment flyers advertising the study will be posted within MUSC among general population patient clinic waiting room and elevator areas. Study recruitment will also take place in the clinics of MUSC and via referral during an admission for COPD exacerbation, or within the first 2 weeks after discharge. Any MUSC clinician who provide care to the target population can initially approach potentially eligible patients about the study, and if interested provide them with the contact details for the Study Team. With the patient's verbal permission, the provider may also provide the patient's contact information to the Study Team. Upon initial contact with the patient, patients will be verbally prescreened per the inclusion/exclusion criteria by our study team and given more information about the study. For those prescreened eligible and interested patients, and an informed consent meeting will be set-up at MUSC Nexus Research Center at the patient's convenience.

Additionally, for the purposes of this study and in direct alignment with the mission of the CON P20 Symptom Self-Management Center, we will employ the use of MUSC Bioinformatics Center (BMIC) core services to identify and recruit patients across the MUSC Enterprise that meet the study inclusion/exclusion criteria and that have granted authorized research contact permission in MyChart through the electronic 'opt in' EPIC designation. Once these potentially eligible patients are identified, we will then contact them by telephone using a script to determine if they are interested in study participation.

## 9.0 Consent Process

Research activities will not be conducted without the patient's written informed consent. Informed consent will be conducted by the PI and/or their designee as noted on the study delegation log, and will occur in the comfort and safety of a private clinic room prior to any screening procedures being conducted and/or data collection. Potential participants will be given the informed consent document to read and review in advance, and/or may have it read to them by the researchers, if they prefer. After reviewing the consent document, the patient will be given the opportunity to ask any questions about the study that they may have, and will be requested to demonstrate what is expected from them should they agree to enroll in the study through a questioning of their understanding of study procedures and risks. Prior to consenting, all questions will be resolved to the patient's satisfaction. If a participant does not appear to understand the information contained within the Consent document or of what is expected of them as a study subject, then the study coordinator will review the consent document again with the participant. If after this second review, the subject does not demonstrate an understanding, they will not be enrolled in the study. Only participants, with no observed cognitive impairment, will be consented and enrolled into the study.

The consent form will meet the requirements of the Code of Federal Regulations and the MUSC Institutional Review Board; and, include the following elements:

- The purpose, nature, and objectives, potential risks and benefits of the intended study.
- The length of study and the likely follow-up required.
- The name and a contact of the investigator(s) responsible for the protocol.
- The right of the participant to accept or refuse study interactions and to withdraw from

participation at any time.

All consented subjects will be given a copy of their executed and countersigned Consent form. The researchers will maintain a means of contact with all enrolled study participants in the eventuality that reconsenting of currently enrolled participants is needed and/or the disclosure of new study information is warranted to previously enrolled participants.

## 10.0 Study Design / Methods

This is a randomized longitudinal controlled observational study using a mixture of qualitative and quantitative methods. The study will recruit 30 participants and utilize a control group experimental design with dependent pretest and posttest to derive data regarding (1) feasibility and (2) within-participant effect size of the RESP-FIT intervention in terms of satisfaction, use and adherence, technical issues and acceptability, and self-reported symptom severity (dyspnea and fatigue). In addition, information satisfying Exploratory Aim 4 (frequency of physical activity) will be obtained. Patient data (Table 1 below) will be collected at baseline, 6 weeks (post-treatment) and 14 weeks (2 month follow up). This study will enable further development of SAMS using our patient centered iterative design guided by feedback from a convenience sample. When completed, 30 adults (15 in each group) will have used SAMS for 6 weeks. (see Fig. 2 Study Design).

### Objective Measures:

| Data Collection   | Measures   | Data sources and time points  |
|---|--|---|
| Demographics  | Age, health history, race/ethnicity, rural/urban residence, insurance  | Participant interview and medical records   |
| Clinical Characteristics                                    | FEV1/FVC
Self-reported hospitalizations/exacerbations   | Participant interview and medical records; PFT baseline and at second study visit |
| Maximal Inspiratory & Maximal Expiratory Pressure Generated | MIP and MEP recorded using a calibrated MicroRPM respiratory pressure meter, units in cm H 2 O ; a surrogate parameter for respiratory muscle weakness/strength | Collection and calibration at baseline, and at second study visit.                |
| Physical Activity: Steps                                    | # of steps taken daily (via Fitbit Alta)   | Daily   |
| Physical Activity: Patterns of Active Minutes               | # of minutes active throughout the day (via Fitbit Alta)   | Daily   |
| Sleep   | Hours of Sleep (via Fitbit Alta)   | Daily   |

### Participative Measures:

[figure not shown]
| Data Collection                             | Measures   | Data sources and time points   |
|---|--|--|
| St. George's Respiratory Questionnaire      | Impact of COPD on: 
 
Overall health (symptom severity, symptom frequency)
 
QOL (impact component, activities that are limited by breathlessness, social functioning, psychologic burden)
 
Perceived Well-being
 
 | Participant interview/questionnaire; baseline and after intervention |
| PROMIS v1.0 Fatigue                         | Monitoring of sample representativeness; types of recruitment activities; rates of recruitment; % eligible, consented, provided with informational session   | Participant interview/questionnaire; baseline and at each session    |
| PROMIS v1.0 Dyspnea: Functional Limitations | Functional Limitations   | Participant interview/questionnaire; Baseline                        |
| PROMIS v1.0 Dyspnea: Task Avoidance         | If tasks are avoided
How often tasks are avoided  | Participant self-report; Baseline and at each study visit            |

|   |                                       |   |
|---|---------------------------------------|---|
| PROMIS Self-Efficacy                      | Self-efficacy                         | Participant self-report; Baseline and at each study visit |
| PROMIS v1.0 Sleep Impairment              | Sleepiness during the day; impairment | Participant self-report; Baseline and at each study visit |
| PROMIS v1.0 Sleep Disturbance, short form | Falling asleep                        | Participant self-report; Baseline and at each study visit |

### Other Measures:

|  |  |                                   |
|--|--|-----------------------------------|
| Maintenance:
Projection of future adoption | # COPD patients who would continue intervention;
patient perception of the intervention | Patient interview at end of study |
| Feasibility:                                  | Acceptability, utility of intervention   | Patient interview at end of study |

**Figure 2: Feasibility Study of RESP-FIT with SAMS Report: Pilot Intervention with Quantitative/Qualitative Assessment**

**Participants:** Subjects will be 30 adults, aged 40 and older, with mild to moderate COPD, defined as a spirometric diagnosis of (FEV1/FVC <0.7 and FEV1 % predicted < 50%), with the ability to understand written and spoken English, and who report dyspnea greater than “2” on the Modified Medical Research Council (MMRC). Participants must be willing to continually wear a FitBit activity monitor, and have access to a smartphone or Wi-Fi/Data-enabled iPad and with willingness to download the FitBit and

SAMS apps. Participants without access to a smartphone or Wi-Fi/Data-enabled iPad may be loaned an iPad for the duration of their training and given comprehensive training on the use of the device. Pregnant females and females less than 1 year post-partum (via self-report) will be excluded, as pregnancy affects fatigue and the perception of dyspnea due to increased abdominal pressure on the diaphragm and potential displacement of abdominal organs. Exclusion criteria also include lack of cognitive ability to complete questionnaires, mobility impairments, memory impairments and dementia. We will not exclude participants with comorbid depression or history of substance abuse, as we will be including depression in our analysis as well as to have a representative sample.

**Procedures:** Recruitment for 6-week trial: Study recruitment will take place in the clinics of MUSC as well as by telephone with patients across the MUSC Enterprise that meet the study inclusion/exclusion criteria and have granted authorized research contact permission in MyChart through the electronic 'opt in' EPIC designation. Participants may also be recruited by via referral during an admission for COPD exacerbation, or within the first 2 weeks after discharge. If additional participants are needed, advertisements will be placed at the clinics of MUSC and our team will accept referrals from any MUSC provider regardless of recent hospitalization. Referrals will be screened for eligibility by our study team. An advertisement is included in the IRB submission (see supplemental file "Advertisement").

Technical Training: After receiving complete verbal overviews and signing informed consent (and assent), participants will have SAMS installed on their phone; receive a demo of SAMS. Patients with COPD are commonly instructed on how to perform a peak flow, but our team will ensure they understand this process and if a peak flow device is needed, we will supply this device (e.g., digital or manual peak flow meter depending on availability). Participants will be given our study coordinators and PI's telephone number should technical or procedural questions arise during the study. TACHL staff will take service tech calls, as done on other TACHL studies. Participants will be instructed to carry their phone during waking hours for the 6-week trial and to use the video capture training technique at least 1 time per week during the study period.

**Randomization and Training Regimen:** Following collection of pre-training baseline measures, participants will be randomly assigned 50/50 to either a Standard of Care (SOC) Control Group (n=15), or a SOC + EMST/IMST Group (n=15). Participant randomization will be stratified by gender and dyspnea grade as measured on the MMRC. Those participants assigned to the SOC control group will receive a Fitbit monitoring device, but no intervention beyond that which is typically provided to patients seen within the MUSC Clinic. Participants randomly assigned to receive SOC+EMST/IMST will receive six weeks of clinician-guided, scripted RMST. This training will be facilitated by the PI using a custom-designed and constructed EMST/IMST trainer. Non-invasive measurement of maximum expiratory and inspiratory pressures (PEmax and PImax; described previously) will be obtained in order to set pressure threshold of the EMST/RMST device. The first week of EMST/IMST training will be conducted with the device set at 75% of the average initial PEmax collected at pre-training baseline. After a nose clip is placed the participants will be taught a four-step procedure: 1) take a breath in, 2) wrap lips tightly around the EMST/IMST trainer mouthpiece, and 3) exhale quickly and forcefully until you hear the popping or whistling sound of the device valve opening, and 4) continue blowing forcefully for two seconds. Once the participant is able to do a five-breath trial, another five-breath trial will be completed with the participant allowed as much independence as appropriate. The participant will receive a text message each day reminding them to complete his or her training and "remain active today." Participants in the SOC group will receive a text message reminding them to "remain active today." The daily training session will be as follows: 1) five sets of five-breath exhalations (25 breaths total) completed each training day, 2) each exhalation within a set will be separated by approximately one minute, and 3) each five-breath training set will be separated by five minutes. A Bluetooth-enabled "use" button on the EMST/IMST device will log the times the participant has used their training device. Each participant will be provided with a diary to record five sets of five-breath training trials on five days each week. Our experience indicates that EMST/IMST takes approximately 20 minutes each day. PEmax will be reassessed weekly, by the research clinician across the six-week treatment period and readjusted to 75% of the participant's current PEmax. If no changes in PEmax are observed week to week, treatment

will be continued without increase in the pressure threshold training level. All participants will be managed according to standard treatment protocols used within the MUSC Pulmonary Clinic. Detailed records will be kept pertaining to mortality and morbidity as well as use of inpatient and outpatient hospital facilities, medication use, frequency and duration of disease exacerbations, as well as general response to treatment. All dependent variables will be obtained, for all participants at baseline, mid-intervention (3 weeks post baseline), at intervention end (6 weeks) and 14 weeks (2 months) post baseline.

**Monitoring period:** As per our standard monitoring period with SAMS, participants will receive a daily EMA reminder text. Answering the EMA questions on a smartphone requires 30-45 seconds of time. Probes will occur to not interfere with typical sleep schedule or during school hours. EMA sessions will capture COPD symptoms and emotion/mood over the course of the day. If patients have not filled out an EMA in 3 days, a reminder text will be sent. EMA probe question responses will transfer to RedCap, as TACHL has done with other studies. Data will not be stored on the phone. The participants will be requested to perform video capture of training technique 1 time per week. A reminder will be sent during convenient waking hours if this has not been performed.

**Activity Tracking:** A Fitbit activity tracker will be provided to each participant and comprehensive instruction offered on its use. This activity tracking device is worn on the wrist and only removed for bathing or other activities involving water, as the devices are water-resistant but not waterproof.

**Quantitative and Qualitative Assessments:** Participants will complete quantitative and qualitative assessments of acceptability, feasibility, and performance of the SAM system including:

Assessments/Measures. 1) Enrollment Screening and Assessments. During the screening: demographic data, current prescription for COPD controller medication, general medical history including COPD severity and co-morbid conditions, access to mobile technology, contact information to schedule final visit, and most recent ambulatory visit will be collected. For patients that meet inclusion/exclusion criteria during the enrollment encounter, validated surveys on self-efficacy (e.g. PROMIS Self-Efficacy), and COPD symptoms (e.g., St. George's Respiratory Questionnaire) will be also administered. In accordance with our P20 center, PROMIS measures (Pain, Fatigue, Dyspnea, Task Avoidance) will be administered.

2) EMA Questions (see attachment for details). As per previous SAMS study, questions will assess: COPD symptoms (cough, wheeze, mucus), emotional status/mood (happy, angry, anxious, stressed, relaxed, and bored; 0=not at all, 4=extremely), and scheduled COPD preventive care and health seeking behavior questions. 3) Acceptability Ratings (initial visits and at 2 mo): The Mobile App Rating Scale will assess the following aspects of SAMS: a) engagement (including fun, interest, customization, interactivity, and target audience) b) functionality (performance, ease of use, navigation, design) c) aesthetics (layout, visual appeal, color, and style) d) information (accuracy, goals, quality, quantity, clarity and credibility). 4) Quantitative outcomes: During the final visit validated surveys on adherence (e.g., Self-report Adherence), self-efficacy (e.g. PROMIS Self-Efficacy), and COPD symptoms (e.g., St. George's Respiratory Questionnaire) will be administered and compared to the enrollment survey responses.

One time per week of the study, the patients will be requested to perform video capture of training technique that will be reviewed by our PIs to determine beneficial elements of this video. If applicable, we will also compare return visits to the emergency department and hospital between previous enrollees in the last version of SAMS in a pediatric population. This "on the shelf data" of previous enrollees will be compared to the new enrollees with telehealth visits. 5) Qualitative Key Informant Interviews Qualitative data will be obtained via open-ended interview questions on the acceptability topics above. Interviews will be recorded for transcription and qualitative analyses will be applied using qualitative software program to determine themes in participant responses, which will prompt modifications to the SAMS program. Interviews may be performed over the phone if convenient for the family.

**Participant Compensation:** Participants will receive \$25 for screening, and \$25 at the initial enrollment visit for completion of the initial enrollment assessment and surveys (total of \$50 if enrolled). Additionally,

at the post study evaluation, they will receive up to \$75 for logging into app, wearing their Fitbit, and bringing back the study devices (e.g., Fitbit), completing EMA and surveys, and the brief key informant interview. Final visit compensation will be based on adherence to the study protocol including symptom data entry, EMA reports, telehealth visit, and final visit surveys/KIIs. Each day will be valued at \$2.50 and reimbursement will depend upon adherence to the study protocol including ensuring EMA symptom and training data is available for 5 days manually (for a total of \$12.50/week) for a total of \$75 over the six-week period. Tracking of reimbursement amount during the study will be delivered via the App in a compensation log. \$50 will be reimbursed for completing Visit 2 at Week 6, and another \$50 for completing the two-month follow-up visit. Total up to \$225 = \$75 (EMA and training data \$12.50/week x 6 weeks) + \$50 at Visit 1 + \$50 at Visit 2 + \$50 at Visit 3.

